7.11.1 Primary Efficacy Evaluations

For primary efficacy measures based on oxygenation parameters, the main timepoints of interest for analyses are baseline, up to Day 6 for P(A-a)O₂ gradient, and by Day 14 for rate of intubation, where data are available, unless otherwise specified.

See Sections 7.1.2, 7.1.3, and 7.1.4 for algorithm on determining assessments to be used for analysis.

As ABG was required only at baseline and at Day 6/Post-Treatment visit (or day of discharge if earlier), the number of patients with complete data at all study visit days is expected to quite limited. Therefore, the primary timepoint for analyses for data based on ABG will be up to Day 6.

7.11.1.1 Oxygenation Up to Day 6

The $P(A-a)O_2$ gradient will be derived using arterial blood gas assessment via arterial puncture at baseline and up to Day 6, or day of discharge whichever is earlier. See Sections 7.1.2, 7.1.3, and 7.1.4 for algorithm on determining assessments to be used for analysis.

The change from baseline and percentage from baseline is defined as:

Percentage Change from Baseline= Change from Baseline/ Baseline

The P(A-a)O₂ gradient, the percent change from baseline up to Day 6 will be tabulated based on "unchanged or deteriorated" [no difference or positive percent change from baseline] and "improved" [negative percent changer from baseline] by 10% change increments. In addition,

the percentage of patients with $a \ge 33\%$ improvement for each treatment arm will be provided. For both of these analyses, a Chi-square, or Fisher's exact test (or stratified logistic model) will be generated to compare the treatment arms. Alternative cutoffs for defining meaningful improvement may be used (e.g., 25%, 50%), with similar analyses methods as above.

The maximum change from baseline and maximum percentage change from baseline will be summarized up to Day 6, and for the study duration.

Maximum percentage change from baseline is defined as:

Maximum Percentage Change from Baseline= Maximum Change from Baseline/ Baseline

For these analyses, the baseline is defined as the last available assessment prior to administration of study drug (see Section 7.1.2 above). Except as noted in Section 7.1.1, unscheduled records will be excluded from the summaries at specific timepoints but will be included in the maximum change from baseline.

A listing of all P(A-a)O₂ gradient measurements will be provided.

A Mixed Model Repeated Measures (MMRM) model will be used to evaluate the change in $P(A-a)O_2$ gradient, in which the change of $P(A-a)O_2$ gradient from baseline on each study day up to Day 6 (or day of discharge) will be included as dependent variable and treatment, study day (categorical), and treatment-by-study-day as fixed effects, patient as random effect, and the baseline value as a continuous covariate. An unstructured covariance matrix will be used for the MMRM analysis, unless the model does not converge, in which case the compound symmetry will be used. The change in $P(A-a)O_2$ gradient up to Day 6 will be evaluated by this MMRM model.

Change in oxygenation/respiratory parameter of P(A-a)O₂ gradient will also be presented by waterfall plot.

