7.1 General Considerations

All safety analyses will be based on Safety Population; all efficacy analyses will be based on Modified Intent-to-Treat population, unless otherwise specified. Some specific sensitivity analyses of efficacy may be based on ITT and Per Protocol populations (for primary endpoints only). See Section 7.4 below for definitions of each analysis population.

All analyses will be considered as descriptive analyses. Derivation of two-sided 95% confidence intervals and p-values will be generated where applicable.

Time to event endpoints will be defined as the start date/time to the end date/time; censoring dates will be the last date/time the patient was determined to be event-free. Kaplan Meier methods will be used for time to event endpoint analyses; a log-rank test will be performed to compare the two survival curves. Timepoints estimates and median survival will be derived from the Kaplan Meier analysis. A Cox proportional hazards model may also be used to compare the two treatment arms using a hazard ratio.

Categorical endpoints will be calculated as the percentage of patients with the event, relative to the number of patients in a given analysis population (see Section 7.4). Stratified logistic regression approaches and/or repeated measures statistical approaches may be used to compare patients on the sargramostim and control arms, in addition to Fisher's Exact or Chi² tests (as appropriate). The randomization stratification factor for the baseline SOFA score (<6 versus \geq 6) will be considered for any stratified analysis.

Continuous endpoints will be summarized by n, means, medians, minimum, maximum, and 25th and 75th percentiles. Analysis of variance, analysis of covariance, and/or repeated measures statistical approaches may be used to compare patients on the sargramostim and control arms.

In the event that the underlying assumptions and/or distributions for a given statistical method are not satisfied, alternative statistical methods will be employed.

Additional exploratory analyses may be performed to evaluate the robustness and sensitivity of the study results, including but not limited to, additional evaluation of endpoints on other

analysis populations, subgroup analyses, treatment interactions, adjusted or stratified analyses, and/or alternative statistical methods.

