7.2 Sample Size

Approximately 120 patients will be randomized: of which 80 will receive sargramostim + SOC, and 40 patients who will receive SOC alone to evaluate the clinical efficacy and safety of sargramostim in patients with COVID-19 associated acute hypoxemia.

The sample size was based on practical and clinical considerations to ensure that the efficacy endpoints and safety profile could be appropriately evaluated and was not based on any statistical assumptions or hypotheses. As a result, the analyses of this study will be considered as descriptive analyses.

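### The ≥33% P(A-a)O₂ responder comparison leaves out the baseline gradient that the MMRM of the same endpoint includes; adding it costs almost nothing and may gain precision

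*SAP*

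**What the plan says.** SAP 7.11.1.1 derives each patient's percent change in P(A-a)O₂ up to Day 6 and tabulates it in 10% steps. It then adds the share of patients with at least a 33% fall: "improvement for each treatment arm will be provided". Cutoffs of 25% and 50% are named as possible alternatives. On the test it says: "For both of these analyses, a Chi-square, or Fisher's exact test (or stratified logistic model) will be generated to compare the treatment arms". It does not say which of the three governs, or what the logistic model contains beyond its strata.

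Section 7.1 indicates what a stratified analysis would use: "The randomization stratification factor for the baseline SOFA score", split at 6. The baseline gradient is not mentioned there.

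The MMRM paragraph of 7.11.1.1 models change in the same gradient with "patient as random effect, and the baseline value as a continuous covariate".

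On status, section 7.1 says "All analyses will be considered as descriptive analyses", but also "Derivation of two-sided 95% confidence intervals and p-values will be generated where applicable". Section 7.2 says the sample size "was not based on any statistical assumptions or hypotheses".

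**The concern.** Dividing by baseline does not make percent change independent of baseline. If patients who start with a high gradient are more (or less) likely to reach a one-third fall, a chance difference in starting gradient between the arms moves the responder difference. The MMRM removes that component and the responder comparison does not, so the two analyses of one primary endpoint can diverge for this reason alone.

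The baseline value is already needed to compute percent change. Leaving it out of the model therefore gives up information in hand, in a trial of about 120 patients with only 40 controls.

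**Working it through.** The SAP states no power, effect or correlation, so there is no planned figure to reproduce. The check asks how much the missing covariate could matter.

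**Inputs from the SAP.** Section 7.2: "Approximately 120 patients will be randomized: of which 80 will receive sargramostim + SOC, and 40 patients who will receive SOC alone". The working level is two-sided 0.05, in line with the 95% intervals of section 7.1. The responder cutoff is a 33% fall.

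**Assumptions (not in the SAP).** Responder rates 25% control and 50% treated; complete data; log-normal gradient with CV 0.4 to 0.6; correlation ρ between log baseline and log follow-up; k = follow-up log SD / baseline log SD.

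**Step 1: unadjusted power.** Pooled rate = (80×0.50 + 40×0.25)/120 = 0.417. SE under the null = √(0.417×0.583×(1/80+1/40)) = 0.0955. SE under the alternative = √(0.25/80 + 0.1875/40) = 0.0884. Power = Φ((0.25 − 1.96×0.0955)/0.0884) = Φ(0.71) = 0.76.

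**Step 2: when response depends on baseline.** The correlation of the log ratio (follow-up/baseline) with log baseline is

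r = (ρk − 1)/√(1 + k² − 2ρk).

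A negative r means that a high start favours response. It is zero when ρk = 1 and positive when ρk > 1.

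**Step 3: power, simulated at 80 v 40.** The adjusted test is the likelihood-ratio test from logistic regression with log baseline.

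| ρ | k | r | chi-square | adjusted | gain (points) |
|---|---|---|---|---|---|
| 0.3 | 1 | −0.59 | 76–77% | 87% | +10 to +11 |
| 0.5 | 1 | −0.50 | 75–77% | 83–85% | about +8 |
| 0.7 | 1 | −0.39 | 76–77% | 81–82% | about +5 |
| 0.85 | 1 | −0.27 | – | – | about +3 |
| 0.9 | 1 | −0.22 | – | – | about +2 |
| 0.5 | 1.5 | −0.19 | 75.6% | 77.8% | +2.2 |
| 0.5 | 2 | 0 | 76.1% | 77.0% | +0.9 |
| 0.7 | 1.4 | −0.02 | 76.3% | 77.3% | +1.0 |

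The rows with r = 0 or −0.02 still show about 1 point. That is a small difference between the two tests, not baseline information, so the low end of the range is close to no gain.

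**Step 4: other assumed models.** With normal gradients (mean 350, SD 100, correlation 0.2 to 0.9), the gain over chi-square was 0.9 to 7.6 points. With rates of 30% v 50% or 30% v 57% and the baseline effect set directly, it ran from 1.2 or 2.2 points at no association, through 9.4 or 7.3 at a log-odds of 1.0 per SD, to 22.6 or 14.5 at a very strong 2.0 per SD. A SOFA-like binary stratum (assumed latent correlation about 0.5 with the gradient) gained only about 1.5 to 4.6 points in that model, little more than the no-association level.

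**Step 5: type I error.** Under the null, chi-square rejected between 4.3% and 6.5% of the time across all runs, and the adjusted test 4.7% to 6.6%. With 1,500 null trials the simulation SE is √(0.05×0.95/1500) = 0.6 points, so both are near nominal.

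**Step 6: size of the imbalance effect.** The SD of the between-arm difference in mean baseline is √(1/80+1/40) = 0.19 patient SDs. At ρ = 0.5 and k = 1 its correlation with the responder difference is 0.36. A one-SD chance imbalance therefore moves the difference by 0.36×8.84 = 3.2 percentage points, against a standard error of 8.8. At ρ = 0.7 and k = 1.8 the correlation is −0.14, so the direction reverses.

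**The case against.** A chi-square or Fisher test of randomised proportions is valid, and the simulations confirm it. The main analysis of the continuous endpoint already adjusts for baseline, and the responder percentage is presented as an addition to it. The trial is declared descriptive, so there is no power target to miss. Section 7.1 also leaves room for adjusted analyses. All of this stands, and it limits the point to an improvement rather than an error.

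It does not remove the point. The responder comparison will carry its own p-value, and a descriptive estimate also benefits from precision. The adjusted analyses in section 7.1 are optional and exploratory, so whether to adjust could be decided after the data are seen.

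A reader might infer four stronger things that the SAP does not support:

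- **That the comparison is simply a crude test.** A stratified logistic model is listed as an option; it is just not fixed and does not name the gradient.
- **That the result is biased or the error rate inflated.** Randomisation protects both.
- **That the loss is 5 to 14 points of power.** The lower end requires equal spread at baseline and follow-up. The upper end compares against Fisher, where about 3.5 points of the difference appear even with no baseline association.
- **That imbalance always favours the arm that started worse.** When follow-up is sufficiently more variable than baseline, the effect vanishes or reverses. That is plausible here, since patients enter hypoxemic and then recover or deteriorate.

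**Conclusion.** The point holds as a low-cost improvement. No listed option for the ≥33% comparison (or a 25% or 50% cutoff) includes the baseline gradient, while the MMRM of the same endpoint does. The consequence is lost precision and chance imbalance left in the estimate, not bias.

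Under assumed rates of 25% v 50% the power gain over chi-square is about 1 to 11 points, and where it falls in that range depends on ρ and k, which the SAP does not give. Steeper assumed baseline effects at other responder rates give larger gains, but nothing in the SAP supports relying on them.

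**What to change.** In 7.11.1.1, name one responder analysis in advance: logistic regression with treatment, continuous baseline P(A-a)O₂ and the SOFA stratum (<6 v ≥6), applied equally to any alternative cutoff. Report the covariate-standardized risk difference with its 95% CI, because the adjusted odds ratio is conditional on the covariates and does not translate directly into the difference in percentages. Keep chi-square or Fisher as the unadjusted companion, and state which of those two is used.

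A proportional-odds model for the 10% tabulation is optional and not needed.

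The cost is a few lines of SAP text and one model statement. No patient is lost by adjusting for the gradient, since percent change cannot be computed without it, and SOFA is already a randomization stratum.

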The purpose of this statistical analysis plan (SAP) is to describe the procedures and statistical methodologies that will be used in the analysis and reporting of results for Partner Therapeutics Protocol PTX-001-002.

This document is prepared based on the following documents:

- the study protocol version 2.0 dated 02 December 2020;
- the Case Report Form version 1.7 dated 08 January 2021.

Readers are referred to the final study protocol (and any amendments or addenda), the case report form (CRF), and CRF completion guidelines for details of the study design, conduct and data collection. Any significant changes to these documents in terms of the principal features of the study analyses may result in an SAP amendment; any other changes will be denoted in the Clinical Study Report as changes to the planned analyses.

This SAP must be finalized prior to the locking of the clinical database for this study. The mock summary tables, figures and by subject data listings (TFLs) are provided in a separate document.

5 Study Objectives and Endpoints

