6.1 Study Design Overview

This study is a randomized two-arm open-label study. This Phase 2 study will randomize approximately 120 patients with COVID-19: of which 80 will receive sargramostim + SOC, and 40 patients who will receive SOC alone. Refer to Section 5.1 of the Study Protocol for a more detailed description of the study. Section 1 of the Study Protocol is a schematic of the study design.

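### SAP Section 7.11.1.1 plans three between-arm comparisons of the primary P(A-a)O2 endpoint, names none of them as primary, and leaves the list of responder cutoffs open

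*SAP*

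**What the plan says.** Section 5.2.1 makes change in P(A-a)O2 gradient by Day 6 a primary endpoint, alongside intubation by Day 14. Section 7.11.1.1 then sets out the following for the gradient:

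- **10% categories.** Percent change is tabulated as unchanged or deteriorated, or as improved in steps of 10%.
- **33% responders.** The proportion improving by at least 33% is given for each arm. For this and the categories, the method is a chi-square test, Fisher's exact test "or stratified logistic model) will be generated to compare the treatment arms". No rule chooses among the three.
- **Further cutoffs.** "Alternative cutoffs for defining meaningful improvement may be used (e.g., 25%, 50%), with similar analyses methods as above".
- **MMRM on change.** The change in the "gradient up to Day 6 will be evaluated by this MMRM model". The paragraph does not say whether the reported contrast is the overall difference or the difference at Day 6.

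Maximum change is summarized and a waterfall plot is shown, but no between-arm test is attached to either.

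On inferential status, Section 7.1 states "All analyses will be considered as descriptive analyses", followed by "Derivation of two-sided 95% confidence intervals and p-values will be generated where applicable". Section 7.2 says the sample size "was not based on any statistical assumptions or hypotheses". Section 6.1 gives the design: "This study is a randomized two-arm open-label study". The introduction, just before Section 5, sets the timing: "This SAP must be finalized prior to the locking of the clinical database for this study".

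**The concern.** A primary endpoint needs one analysis that is known in advance to be its answer. Here three comparisons are promised, and a fourth group can be added without limit because 25% and 50% are only examples. The permission to add cutoffs also outlives the SAP's own deadline. A SAP finalized before database lock with this sentence in it still allows a new cutoff to be tested afterwards. A reader shown a nominal p-value at one cutoff could not tell how many others were tried.

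The secondary ordinal scale is fixed more tightly. Section 7.11.2.1 specifies the overall LS mean difference from its MMRM, with 95% CI and p-value, whereas the primary endpoint's MMRM paragraph specifies no contrast.

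At stake is how much weight a nominally significant oxygenation result can bear. A difference at a cutoff picked from several looks stronger than it is.

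**Working it through.** **No figure to reproduce.** The SAP states no alpha, power, effect size or SD. The 5% two-sided level used below is inferred from the 95% intervals in Section 7.1.

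**Inputs from the SAP.** Arms of 80 and 40 (Section 7.2). Firm comparisons: 10% categories, 33% responders, MMRM. Optional comparisons: the 25% and 50% cutoffs.

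**Simple upper reference.** If k tests were independent, the chance of at least one p<0.05 would be 1 - 0.95^k:
- k = 3: 1 - 0.8574 = 14.3%
- k = 5: 1 - 0.7738 = 22.6%

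These tests share the same data and are correlated, so the true figure is lower and has to be simulated.

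**Assumptions (none from the SAP).**
- Baseline B is lognormal, median 250, log-SD 0.45.
- Percent change is normal, floored at -95%, with (mean, SD) of (0, 40), (-15, 40), (-25, 40), (-30, 30) or (-10, 60), the same in both arms.
- Each pair is run with and without dependence on baseline: with r = 0 or 0.5, the term r × SD × (ln B - ln 250)/0.45 is subtracted.
- Arms are 80 v 40, or 60 v 30 to allow for missing blood gases.
- This gives 5 × 2 × 2 = 20 scenarios, with 20,000 null trials in each.

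**Tests.**
- *Change.* ANCOVA of change (B × percent change/100) on arm and baseline, standing in for the MMRM. Section 7.11.1 requires blood gases only at baseline and Day 6, so this is a reasonable approximation.
- *Cutoffs 25%, 33%, 50%.* z = (p1 - p0)/√[p(1-p)(1/n1 + 1/n0)], significant if |z| > 1.96.
- *Categories.* Pearson chi-square on one unchanged-or-deteriorated group plus the 10% improvement bands.

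**Results, range over the 20 scenarios.**

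| Null event | Rate |
|---|---|
| ANCOVA alone, p<0.05 | 4.8-5.2% |
| 33% cutoff alone | 4.5-5.3% |
| 10% categories alone | 3.1-4.5% |
| At least one of the three firm tests | 10.5-11.6% |
| At least one of five (adding 25% and 50%) | 13.8-15.7% |
| At least one result favouring sargramostim, ANCOVA and three cutoffs | 5.6-6.5% |

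The last row compares with 2.5% for a single two-sided test read in one direction. A separate simulation (4,000 null trials in each of two scenarios) gave about 11%, 15% and 6-7% for the last three rows. With Fisher's exact test at the cutoffs, the five-test rate falls to about 13-14%.

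**Relative size.** 11/5 = 2.2 times nominal for the firm plan and 15/5 = 3 times with the two example cutoffs. In the favourable direction the ratio is about 6/2.5 = 2.4.

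**Left out.** Other cutoffs, a free choice among test methods, the ITT and PP repeats (Section 7.11.1.3) and the intubation comparison. Each added test can only raise the chance of at least one nominal result.

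**The case against.** The strongest reply is that the plan claims no error rate. It declares every analysis descriptive, sets no alpha and bases its sample size on no hypothesis. That stands: no stated rate is breached. It does not settle the matter, because the plan still commits to comparative tests of a primary endpoint.

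Second, the MMRM is the only test applied to the change itself, which is the endpoint as worded, while the categories and cutoffs use percent change. This largely stands, and it is why the fix builds on the MMRM. What is missing is the designation as primary and the contrast.

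Third, the 33% proportion must be reported whatever else is shown, and displaying other thresholds is a normal check on a responder result. This also stands. Other cutoffs add to 33% and do not replace it. The problem is attaching p-values to an open list.

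Some stronger readings are tempting but unsupported:

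- **Five tests are planned.** Only three are firm; 25% and 50% are optional examples.
- **The open-label design produces the 11% or 15%.** Blinding plays no part in the calculation. It matters only because it makes selection with results in view easier.
- **The authors chose cutoffs knowing results by arm.** The SAP does not say so, and its finalization rule does not show it.
- **A development decision rests on these p-values.** The only stated consequence is in Section 7.11, where exploratory endpoints are summarized if primary and secondary results are meaningful, a term left undefined.

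**Conclusion.** The point holds in limited form. The primary oxygenation endpoint has three planned comparisons, no designated primary analysis and an open list of additional responder tests. The chance of at least one nominal p<0.05 under no effect is about 11% for the firm plan and about 14-16% with the two example cutoffs. Chance findings in favour of sargramostim run at about 6-7% on the four directional tests, against 2.5% for one.

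These rates are simulation results under assumed distributions, with ANCOVA in place of the MMRM. The 11% and 14-16% count results in either direction. They describe how far a selected p-value could mislead and do not show that the plan violates an error rate it set. The trial remains interpretable; this is an inexpensive improvement to how its primary result is fixed in advance.

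**What to change.** 1. In the MMRM paragraph of Section 7.11.1.1, name the treatment difference at the Up to Day 6 timepoint, with 95% CI, as the primary analysis of P(A-a)O2. Add the SOFA randomization stratum (<6 v ≥6, Section 6.2) as a covariate; Section 7.1 already singles out this factor for stratified analyses.
2. Delete the sentence on alternative cutoffs, or restrict it to display without p-values, for example a cumulative-distribution plot of percent change by arm.
3. Keep 33% as the only cutoff with a p-value.
4. Label the 10% categories, the 33% table and the waterfall plot as supportive.

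With one designated test, the null rate for the primary analysis returns to about 5% (4.8-5.2% for the stand-in above). The cost is SAP wording, one added model term and fewer p-values to quote. No new data are needed and every planned display is kept.

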7.11.2.3 Time to Improvement in Oxygenation

The secondary endpoint of time to improvement in oxygenation will be assessed in terms of the analysis in oxygenation parameters by visit. That is, evaluation of an improvement in oxygenation parameters will be assessed on the basis of the change from baseline analysis at the study timepoints of interest.

Oxygenation parameters including PaO_2/FiO_2 ratio, SpO_2/FiO_2 ratio and $P(A-a)O_2$ gradient (alveolar-arterial) will be measured at the Screening visit, any days the patient is hospitalized (and where data is available) from Day 1 through Day 28 and at Day 90. On days where arterial blood gas test data is not available, PaO_2 may be estimated using pulse oximetry when required for calculating the PaO_2/FiO_2 ratio.

Oxygen saturation (SpO₂), SpO₂/FiO₂ ratio, and PaO₂/FiO₂ ratio will be summarized, along with the change from baseline and percentage change from baseline, and at all available study visits during Days 1-6, Day 14, Day 28, and Day 90 (where available). See Sections 7.1.2, 7.1.3, and 7.1.4 for algorithm on determining assessments to be used for analysis.

Percentage change from baseline is defined as:

Percentage Change from Baseline= Change from Baseline/ Baseline

For the percent change from baseline in these parameters, deterioration is defined as a negative percent change from baseline, while improvement is a positive percent change from baseline.

Change in PaO₂/FiO₂ ratio will also be presented by waterfall plot.

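### The primary P(A-a)O₂ model uses every study day to Day 6 although blood gases were required only at baseline and Day 6 or discharge, and it names no treatment contrast

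*SAP*

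**What the plan says.** The continuous primary measure is the change in P(A-a)O₂ gradient by Day 6 (SAP Section 5.2.1). Five parts of the SAP decide how it is analysed.

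- **Schedule.** Section 7.11.1 gives the sampling rule first: "As ABG was required only at baseline and at Day 6/Post-Treatment visit (or day of discharge if earlier". From this rule the section forecasts sparse daily data, in that "the number of patients with complete data at all study visit days is expected to quite limited". It concludes that "the primary timepoint for analyses for data based on ABG will be up to Day 6".
- **Source of the gradient.** Section 7.11.1.1 derives it from "arterial blood gas assessment via arterial puncture at baseline and up to Day 6, or day of discharge whichever is earlier". Section 7.11.2.3 lets pulse oximetry stand in for PaO₂ only in the PaO₂/FiO₂ ratio, so it does not supply a gradient on days without an ABG.
- **Endpoint value.** Section 7.1.4 defines the Up to Day 6 evaluation by a window after the end of treatment (24 hours after the last dose on sargramostim; a one-day rule for controls). If the window is empty, the last earlier post-baseline value is used. Section 7.1.5 repeats that fallback and otherwise rules out imputing the gradient.
- **Model.** The MMRM in Section 7.11.1.1 takes the change in "gradient from baseline on each study day up to Day 6 (or day of discharge) will be included as dependent variable". Its terms are treatment, categorical day, their interaction and baseline. On covariance it says: "An unstructured covariance matrix will be used for the MMRM analysis, unless the model does not converge", with compound symmetry as the fallback. The paragraph assigns the change up to Day 6 to this model but names no contrast.
- **Unscheduled values.** Section 7.11.1.1 says "unscheduled records will be excluded from the summaries at specific timepoints", apart from the relabelling allowed in Section 7.1.1. The MMRM paragraph does not say whether they enter the model.

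**The concern.** Section 7.11.1 reasons from a sparse ABG schedule to a single post-baseline timepoint. The MMRM then asks for a daily profile, which that schedule does not provide. The two are different data sets. For example, a patient discharged on Day 4 has a required ABG that day. Under Section 7.1.4 that can be the endpoint value; in the MMRM it is a Day 4 record with Day 6 missing.

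The unnamed contrast adds to this. The closely parallel MMRM for the ordinal scale (Section 7.11.2.1) reports an overall effect first and makes by-timepoint differences optional. Reading the gradient model the same way is plausible, and the effect would then be an average over days that are mostly unscheduled. Apart from discharge-day samples, those days hold a value only when someone chose to draw an ABG, and in an open-label study (Section 6.1) that choice could differ by arm. The MMRM treats undrawn days as missing at random.

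This is the only model the SAP names for the continuous change in gradient, so an average of this kind could partly reflect who was sampled and not only the effect of sargramostim.

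**Working it through.** **No figure to reproduce.** Section 7.2 says the sample size rests on no statistical assumptions. The SAP gives no SD, effect size, within-patient correlation or ABG sampling rate. The size of the problem can therefore only be illustrated under assumptions.

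**Inputs from the SAP.** 80 versus 40 patients (Section 7.2); two-sided 95% intervals and p-values (Section 7.1); the MMRM terms and both covariance structures (Section 7.11.1.1).

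**Assumed inputs.** Changes at Days 2 to 6 with residual SD 1; within-patient correlation 0.7; baseline slope −0.4; Day 6 ABG present in 90%, missing at random; no true treatment effect.

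**Model.** Changeᵢₜ = μₜ + δₜ·treatmentᵢ + β·baselineᵢ + εᵢₜ, for t = 2,…,6, fitted by maximum likelihood with normal-theory tests at two-sided 5%. Two contrasts are read:

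- average over days: (δ₂ + δ₃ + δ₄ + δ₅ + δ₆)/5
- Day 6: δ₆

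In the average, 4 of 5 terms (80%) come from days on which an ABG was not generally required.

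**Sampling on Days 2 to 5.** logit P(draw) = a + b·change. Here b = 0 means random draws and b = 1.5 means draws that rise with current severity. A higher change is worse, so a negative false difference favours sargramostim.

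**Results for the average over days** (unstructured / compound symmetry; 200 runs each):

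| Sampling rule | Days 2–5 sampled, active / control | False difference (SD) | Rejection |
|---|---|---|---|
| Random, equal | 30% / 30% | −0.01 / −0.02 | 4.5% / 5% |
| Severity-driven, same rule in both arms | about 34% / 34% | +0.01 / −0.01 | 9.5% / 3.5% |
| Severity-driven in both, more frequent on active | about 58% / 22% | −0.20 / −0.19 | 18.5% / 18% |
| Near-routine on active, severity-driven on control | 73% / 26% | −0.34 / −0.33 | 45% / 45% |
| Severity-driven on active, random on control | 33% / 27% | +0.29 / +0.30 | 43% / 31% |

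A further setting with random but unequal rates (50% / 20%; unstructured, 400 runs) gave −0.01 SD and 6.5% rejection. Monte Carlo error with 200 runs is about 1.5 points at a 5% rate and 3.5 points at 45%.

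**Day 6 contrast.** Across the 200-run settings it stayed within about 0.02 SD of zero, with rejection of 3% to 8.5%.

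**Reading.** Unequal frequency alone gives no bias, and neither does severity-driven sampling under the same rule in both arms. The bias appears when sampling depends on severity and the rule differs by arm. It sits in the early days: with Day 6 near zero, an average of −0.34 implies about −0.34 × 5/4 = −0.43 SD per early day. Its sign depends on the pattern, and compound symmetry does not remove it.

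**Limits of the check.** Early discharge and the Section 7.1.4 fallback were not simulated. The good behaviour of the Day 6 contrast rests on Day 6 being nearly complete and missing at random.

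**The case against.** The best case for the plan is that it never asks for an average over days. Section 7.11.1 fixes up to Day 6 as the primary ABG timepoint, and the interaction term allows a Day 6 contrast, which the simulations find essentially unbiased. This stands as a possible reading. The SAP does not choose it, though, and its parallel ordinal model points the other way.

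Three stronger readings are tempting and are not supported:

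- *All Day 1–5 values are ad hoc.* They are not, because an ABG on the day of an early discharge is required.
- *The MMRM will produce a false difference.* The SAP specifies no average over days. Nor does it show that ABG ordering follows severity or differs by arm; open-label care only makes that possible.
- *Section 7.11.2.3 schedules a daily gradient and must be amended.* It refers to "any days the patient is hospitalized (and where data is available) from Day 1 through Day 28 and at Day 90". That already carries its own qualifier, and the sentence also covers SpO₂/FiO₂, which needs no ABG.

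It can also be said that excluding unscheduled records would remove most ad hoc values. The SAP states that rule for summaries, not for the model, and Section 7.1.1 allows unscheduled records to be relabelled to a same-day visit. Section 7.1 permits ANCOVA in general terms, and Section 7.11.1.1 also compares arms on categories of percent change, so the MMRM is not the only comparison of the gradient. Neither point settles which continuous analysis is primary.

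Finally, all analyses are called descriptive (Sections 7.1 and 7.2). That limits the consequence, but p-values and confidence intervals are still planned.

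**Conclusion.** The point holds as an unresolved mismatch. The SAP justifies one post-baseline ABG value per patient, then names a daily repeated-measures model for the continuous change without stating the contrast or the handling of unscheduled ABGs.

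The risk of a false arm difference is conditional on an average-over-days reading and on severity-dependent sampling that differs by arm. Under both, with assumed correlation and sampling rates, the illustration gives about 0.2 to 0.3 SD in either direction and 18% to 45% rejection at a nominal 5%. In the settings without bias, rejection for the average was 3.5% to 9.5%. These sizes are not predictions for this trial.

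A Day 6 contrast largely avoids the problem if Day 6 is nearly complete. It still differs from the Section 7.1.4 endpoint for patients discharged early. The matter is worth correcting because the change is cheap and aligns the model with the plan's own endpoint.

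**What to change.** 1. Make the primary continuous analysis an ANCOVA of the change to the single Section 7.1.4 Up to Day 6 value, with treatment and baseline gradient as terms. State which assessment is used if several fall in the window.
2. Keep the MMRM as supportive. Confine inference to the Day 6 contrast, report no average over days, and state whether unscheduled ABGs enter.
3. Tabulate by arm the number of patients with an ABG on each day, and how often the Section 7.1.4 fallback supplies the value. The fallback can still admit a non-required ABG into the ANCOVA, so its use needs to be visible.

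Section 7.11.2.3 needs no change.

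The cost is SAP wording, one simpler model and one table. The downside is that most early non-required ABGs no longer contribute to the primary estimate.
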